#### **6.5 Strata and Covariates**

No stratified analyses or covariate-adjusted analyses are planned for this study.

#### **6.6 Subgroups**

Three pairs of complementary subgroups of patients (for a total of 6 subgroups) will be defined based on receipt of therapy, including anticoagulant therapy, platelet transfusion, and transfusion of any blood product other than platelets, as follows:

- Subgroup 1: Patients who received anticoagulant therapy at any time between 48 hours before and 24 hours after Thrombosomes infusion.
- Subgroup 2: Patients who did not receive anticoagulant therapy between 48 hours before and 24 hours after Thrombosomes infusion.
- Subgroup 3: Patients who received platelets at any time between 6 hours before and 1 hour after Thrombosomes infusion.
- Subgroup 4: Patients who did not receive platelets between 6 hours before and 1 hour after Thrombosomes infusion.
- Subgroup 5: Patients who received any blood product other than platelets at any time between 1 hour before and 24 hours after Thrombosomes infusion.
- Subgroup 6: Patients who did not receive any blood product other than platelets between 1 hour before and 24 hours after Thrombosomes infusion.

Two additional complementary subgroups will be defined as shown below, based on the patient's living status on Day 30 but irrespective of completing the Day-30 visit:

- Subgroup 7: Patients who were alive on Day 30.
- Subgroup 8: Patients who died before Day 30.

Note that the survival outcomes of patients who are alive at last contact but withdraw study participation prior to Day 30 will be considered censored. These patients, consequently, will not be included in either Subgroup 7 or Subgroup 8.

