### 1.9.2.2 Additional Hemostatic Therapy: All Cohorts

This product is not expected to increase the platelet corrected count increment (CCI). The infusion of platelets for six hours prior and one hour after infusion of Thrombosomes is

restricted. However, at any time, if the patient's clinical bleeding remains unchanged or deteriorates with additional or worsening bleeding, the patient's physician(s) may transfuse the patient with blood products, hemostatic agents, or coagulation factors without limitation. The study patient will be followed for safety data for 30 (+2) days post-infusion of the dose of Thrombosomes.

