### **1.11.2 *Exclusion Criteria***

1. Medical diagnosis of acute or chronic DIC (not based on fibrin degradation products alone).
2. PT or aPTT > 1.3 times the upper limit of normal for the laboratory.
3. Past diagnosis of stroke or thromboembolic events including deep vein thrombosis (DVT), pulmonary embolism, venous or arterial thrombosis, blood clots, or transient ischemic attack (TIA), not to include central or peripheral line-related thrombosis.
4. History of major operative procedures that required general anesthesia in the past 2 weeks.
5. A history or diagnosis of immune thrombocytopenia, thrombotic thrombocytopenic purpura, or hemolytic uremic syndrome.
6. Known inherited disorder of coagulation or platelet function (by history).
7. Receiving active treatment with Plavix (clopidogrel bisulfate) or Ticlid (ticlopidine hydrochloride), or other platelet inhibiting therapy.
8. Receiving tranexamic acid or other antifibrinolitics within 48 hours prior to infusion.
9. Receiving active, inpatient treatment full anticoagulation therapy. Note: a heparin flush may be given daily and before and after blood draws to patients with a central line to keep the line patent. Prophylactic anticoagulation is not a contraindication.
10. History of persistent headaches or migraines. Persistent headaches are defined as the headache frequency is 15 or more days a month for longer than 3 months in the absence of organic pathology.
11. History of an MI, stent placement, had valve replacement and/or repair.
12. For patients with an active acute infection, suspected infection, or a single oral temperature of greater than equal to 101°F or a temperature greater than equal to 100.4° F sustained over a one hour period  in the past 24 hours. Fever related either to the patient's underlying diagnosis (cancer or other neoplastic process) or to the treatment of that disease process is

---

 Silberstein SD, et al. Classification of daily and near-daily headaches: field trial of revised IHS criteria. *Neurology*. 1996;47(4):871.

 Freifeld et al. Clinical Practice Guideline for the Use of Antimicrobial Agents in Neutropenic Patients with Cancer: 2010 Update by the Infectious Diseases Society of America. *Clinical Infectious Diseases*. 2011;52(4):e56-e93.

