Routine Chemistry: Na, K, Cl, CO2, Glucose, BUN, Creatinine, Albumin, Total Bili, Ca, AST, Alkaline Phosphatase, ALT, GGT, LDH, Total Cholesterol, Total Protein			X		X	X					
Special Chemistry hsTroponin I or T Assay			X		X	X					
Draw archive sample	X									X	

Evaluation	Initial Screen	Rescreen (if applicable  )	Day 1  Base Line -2 hr pre-infusion	1 hr post infusion ± 15min	6 hr post -1 or +2 hr	Day 2 24 hr post ± 3 hr	If hospitalized			Day 6 (+ 4 days)	Day 30 (+2 days) (by phone)								
							Day 3	Day 4	Day 5										
 Rescreening performed on those patients who passed eligibility criteria, were not actively bleeding at time of initial screen, and started bleeding within 4 weeks. Patients who were initially screened within 4 days (+6 hrs) do not need to be re-screened except for WHO bleeding assessment and CBC.																			
 Baseline may occur on the same day (within 24 hours) as either Initial Screen or Rescreen. The WHO assessment, CBC and coagulation must be collected at baseline, not more than 2 hours prior to infusion. Red cell transfusion must be specifically related to treatment of bleeding within 24 hours of onset of bleeding.																			
 Chart review for SAEs (only) needs to include data from day 1 though Day 30 (+2 days). Phone call with patient is to confirm if the patient had an SAE or required emergency medical care at an outside facility.																			
 Complete physical exam to include height, weight, general assessment of health by history and medical exam including neurological exam. History to include previous transfusion with red blood cells, plasma and/or platelets.																			
 Abbreviated Physical Exam to include general appearance, cardiovascular, respiratory, extremities, abdomen and head and neck.																			
 In the event of the transfusion of a blood component after infusion of Thrombosomes on Days 1-6, CBC results are required from a sample collected within 8 hours or less prior to the transfusion and within 1-hour (+30 min) post transfusion.																			
 Daily CBC required, but ALL CBC data for each patient during the hospitalization phase through Day 6 must be collected and entered into the database.																			
 If TEG or ROTEM testing is available, include samples for the record.																			

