-  Blood products may include packed red blood cells, whole blood, apheresis platelets, pooled whole blood derived platelets, cryoprecipitate, and plasma. In the event of a blood product transfusion occurring after Thrombosomes infusion on Days 1-6, CBC results will be required from a blood sample collected within 8 hours prior to transfusion and within 1 hour (+30 min) following transfusion.
-  Hematology CBC analytes will include WBC, RBC, hemoglobin, hematocrit, platelets, MPV, neutrophils, lymphocytes, monocytes, eosinophils, and basophils. Daily CBC will be required, but all CBC data for each patient during hospitalization through Day 6 will be collected.
-  During screening, coagulation testing will include only PT/INR, aPTT, D-dimer, and fibrinogen. At and following baseline, testing will include PT/INR, aPTT, D-dimer, fibrinogen, TAT, PF 1+2, TEG or ROTEM, and TGA. For baseline testing, PT/INR, aPTT, D-dimer and fibrinogen will be collected no more than 8 hours prior to infusion.
-  EKG measures include only heart rate and QT interval with Fridericia's correction. The EKG will be repeated if performed more than 4 days before infusion.
-  For each of the time-points that require archive samples, 2 10-mL samples will be drawn (1 for plasma and 1 for serum).
-  Medications may include but will not be limited to over-the-counter remedies, herbal preparations, vitamins, supplements and intravenous fluids.
-  Vital signs will include heart rate, respiratory rate, systolic and diastolic blood pressure, and body temperature.
-  Routine chemistry will include Na, K, Cl, CO2, glucose, BUN, creatinine, albumin, total bilirubin, Ca, AST, alkaline phosphatase, ALT, GGT, LDH, total cholesterol, and total protein. Special chemistry will include hs Troponin I and hs Troponin T.

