**Table 3 – List of Nominal Visits and Time-Points**

Nominal Visit/Time-Point	Scheduled Study Day	Day/Time Window
Screening 	Days -28 to Day -1	Any time during Days -28 to Day -1
Baseline	Day 1	Any time pre-infusion during Day 1 
Thrombosomes Infusion	Day 1	None; represents time-point 0 and provides reference for nominal visits and time-points
1-hour post-infusion	Day 1	±15 minutes
6-hour post-infusion	Day 1	-1 to +2 hours
24-hour post-infusion	Day 2	±3 hours
Day 3 	Day 3	Any time during Day 3
Day 4 	Day 4	Any time during Day 4
Day 5 	Day 5	Any time during Day 5
Day 6	Day 6	+4 days (any time during Days 6-10)
Day 30	Day 30	+2 days (any time during Days 30-32)

 If the patient is not actively bleeding at the time of screening but bleeding occurs within 4 days (+6 hours) of initial screening, the patient will not be rescreened (just WHO bleeding severity and CBC assessments will be repeated). If the patient is not actively bleeding at the time of screening but bleeding occurs >4 days and within 4 weeks of initial screening, the patient will be wholly rescreened and, following verification of eligibility, then enrolled and infused.

 Baseline assessments may occur any time preceding infusion on Day 1, except for the assessments of WHO bleeding severity, CBC, and coagulation. These assessments will be required to occur within the 2 hours preceding infusion.

 Relevant only if the patient is hospitalized.

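### The SAP's non-platelet transfusion subgroup can open after the baseline sample has been drawn, and no subgroup marks hemostatic agents or factor concentrates on the coagulation plots

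*SAP*

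**What the plan says.** **Subgroups.** SAP 6.6 forms three received/not-received therapy pairs: anticoagulants (48 h before to 24 h after infusion), platelets, and other blood products. Subgroup 3 is "Patients who received platelets at any time between 6 hours before and 1 hour after Thrombosomes infusion". Subgroup 5 is "Patients who received any blood product other than platelets at any time between 1 hour before and 24 hours after Thrombosomes infusion", and its complement, Subgroup 6, is "Patients who did not receive any blood product other than platelets between 1 hour before and 24 hours after Thrombosomes infusion".

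**Use.** SAP 8.3 turns the three pairs into line colours or patterns, one pair per row, in the second spaghetti panel for ten coagulation measures and three hematology measures. SAP 7.1 also counts patients per subgroup.

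**Baseline timing.** Protocol Table 4, footnote 2: "The WHO assessment, CBC and coagulation must be collected at baseline, not more than 2 hours prior to infusion". SAP Table 3, footnote 2, says of the same assessments: "These assessments will be required to occur within the 2 hours preceding infusion". SAP Table 2, footnote 8, instead allows PT/INR, aPTT, D-dimer and fibrinogen to be drawn up to 8 h before infusion. SAP 6.3 takes the latest pre-infusion value as baseline.

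**Permitted co-therapy.** Protocol 1.9.2.2 restricts platelets from 6 h before to 1 h after infusion. If bleeding is unchanged or worse, the physicians "may transfuse the patient with blood products, hemostatic agents, or coagulation factors without limitation". SAP Table 2, footnote 6, says: "Blood products may include packed red blood cells, whole blood, apheresis platelets, pooled whole blood derived platelets, cryoprecipitate, and plasma". Protocol 1.11.2, item 8, excludes patients "Receiving tranexamic acid or other antifibrinolitics within 48 hours prior to infusion".

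**The concern.** The subgroup rows let a reader see which individual curves carry a co-therapy. There is no control arm, each cohort has 8 patients, and SAP 6.5 plans no stratified or adjusted analysis. These rows are therefore the only planned display that links co-therapy to the coagulation curves. Two things are wrong with them.

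First, the Subgroup 5 window can open after the baseline sample. A product given in between lies inside the baseline-to-1 h comparison, yet the line is drawn in the non-recipient style.

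Second, two of the three classes of treatment named in Protocol 1.9.2.2 have no row. A reader cannot tell from the plot which curves followed a hemostatic drug or a factor concentrate.

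The coagulation measures are a secondary objective in the protocol and are among the primary safety endpoints in the SAP. A movement after infusion could be credited to Thrombosomes when another treatment was given in the same interval.

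**Working it through.** The plan gives no figure of its own here, so the check compares windows and definitions. Times are relative to infusion.

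**Inputs**
- Subgroup 5 window: -1 h to +24 h, length 25 h (SAP 6.6).
- Earliest baseline CBC and coagulation sample: -2 h (Protocol Table 4, footnote 2; SAP Table 2, footnote 2; SAP Table 3, footnote 2).
- Earliest baseline PT/INR, aPTT, D-dimer and fibrinogen: -8 h (SAP Table 2, footnote 8, which conflicts with the line above).
- Patients per cohort: 8.

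**Step 1: uncovered interval.** Earliest baseline lead minus Subgroup 5 lead:
- 2 h rule: 2 - 1 = 1 h.
- Footnote 8: 8 - 1 = 7 h, for those four tests only.

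The anticoagulant window (48 h) and the platelet window (6 h) both open before the 2 h limit. Under that rule, Subgroup 5 is the only therapy window that can open after a permitted baseline sample.

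**Step 2: example.** Baseline coagulation at -2 h, plasma at -1.5 h, no other non-platelet product to +24 h. The plasma comes after baseline and before the 1 h sample. Because -1.5 h is before -1 h, the patient is Subgroup 6 and takes the non-recipient style in row 3.

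**Step 3: conditions.** All three must hold: the product follows the sample that serves as baseline; it is given more than 1 h before infusion; and no other non-platelet product is given from -1 h to +24 h. Because SAP 6.3 uses the latest pre-infusion value, a repeat sample after the product removes the problem for that measure.

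**Step 4: permitted classes against the therapy pairs**

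| Class in Protocol 1.9.2.2 | Therapy pair |
|---|---|
| Platelets | Subgroups 3/4 |
| Other blood products, including plasma and cryoprecipitate | Subgroups 5/6 |
| Hemostatic agents | none |
| Coagulation factors not given as a listed blood product | none |

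Antifibrinolytics in the 48 h before infusion are an exclusion, so for that class the missing row concerns use after infusion.

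**Step 5: size.** One affected patient is 1/8 = 12.5% of the lines in a cohort plot. The documents give no rate of use, so no expected number can be computed.

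**Step 6: after the change.** If Subgroups 5/6 open at the baseline sample, the uncovered interval is 0 h. The window becomes at most 2 + 24 = 26 h under the 2 h rule, or 8 + 24 = 32 h under footnote 8. No change of window brings hemostatic drugs or concentrates into Subgroups 1 to 6; they need their own pair.

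**The case against.** The strongest reply is that little depends on these subgroups. They style lines in plots of individual raw values and feed one count table. No test, endpoint or escalation decision uses them, and the safety package for the data monitoring committee listed in SAP Appendix 1 does not include these plots. Exposure is reported elsewhere: concomitant medications are tabulated by drug class and listed by patient (SAP 7.4), and transfusions are tabulated by product and visit and listed (SAP 9.2). This stands and limits the point to how the plots are read. It does not remove it. Those outputs are not linked to the curves, and the transfusion tables pool the 24 h before infusion as baseline, so they do not show whether a product came before or after the sample.

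The pre-infusion case may also be uncommon. A patient who progresses to Grade 3 bleeding before infusion is not infused, which removes red cells given for such bleeding. The DIC and PT/aPTT exclusions remove some reasons for plasma. This too stands, but red cells for disease-related anemia, plasma and cryoprecipitate remain possible.

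A reader might infer that a patient given a hemostatic drug is mislabelled as untreated. The documents do not support that: the three rows concern anticoagulants, platelets and other blood products, and such a patient is correctly placed in each. A reader might also take 1 h of the 2 h baseline window as a 50% chance of misclassification. It is a ratio of window lengths and says nothing about how often products are given. Nor do the documents say why antifibrinolytics are excluded before infusion, so the exclusion does not show that the protocol regards them as confounders.

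**Conclusion.** Both gaps follow from the definitions, and no other part of the SAP closes them for the plots. Subgroup 5 leaves up to 1 h uncovered under the 2 h sampling rule and up to 7 h for four tests under SAP Table 2, footnote 8; within that interval a recipient can be drawn as a non-recipient. For hemostatic agents and factor concentrates the defect is an absent row.

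Each affected patient is 12.5% of a cohort plot. How many would be affected is unknown, and any share of wrongly labelled lines would rest on an assumed usage rate. The documents also do not establish the direction in which any one agent would move a given marker, so a claim that a false signal or a masked one will result goes beyond them.

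The consequence is confined to descriptive displays. It does not undermine any planned test or the dose-escalation review. It is a low-cost improvement worth making before the plots are programmed.

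**What to change.** 1. Reconcile the 2 h and 8 h baseline sampling rules (SAP Table 2, footnotes 2 and 8; SAP Table 3, footnote 2; Protocol Table 4, footnote 2). Until this is done, the start of the window is ambiguous, because CBC and coagulation baselines may have different times.
2. In SAP 6.6, start Subgroups 5 and 6 at the patient's earliest sample used as a baseline CBC or coagulation value, and no later than 1 h before infusion. Keep the end at 24 h after infusion.
3. Add one complementary pair: received, or did not receive, an antifibrinolytic, another systemic hemostatic agent or a coagulation-factor concentrate from that sample to 24 h after infusion. Take it from the concomitant-medication record and show it as a fourth row in the second panels.
4. State how a Day 1 medication record without a clock time is classed. SAP 6.4 sets a missing start time to the start of the day, which could place a post-infusion drug before the window.

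The cost is SAP wording and programming. Transfusions and concomitant medications are already recorded through Day 6, and no study procedure changes. A fourth row on every second panel adds 10 + 3 = 13 rows. Some subgroups will hold very few patients. If baseline samples have different times, a window set by the earliest one will also flag some products given before the later ones.

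One neighbouring gap stays open: platelets given from 1 h to 24 h after infusion are outside Subgroup 3 and excluded from Subgroup 5. SAP 9.2 plots platelet units separately, so this can be decided in the same revision.

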## 6.7 Multiple Testing

No adjustments or corrections for multiple hypothesis testing are planned for this study.

## 6.8 Significance Level

Unless otherwise specified, all statistical analyses will be performed using two-sided hypothesis testing and a two-sided significance level (i.e., accepted type I error probability,  $\alpha$ ) of 0.05.

## 6.9 Descriptive Statistics and Notation

Unless stated otherwise, the term "descriptive statistics" refers to frequencies (counts and percentages) for categorical data and the number of patients (or samples), mean, median, standard deviation, interquartile range, minimum, and maximum for continuous data. When fewer statistics are needed for continuous variables and the appropriate (or desired) measure of centrality is the mean, the 95% confidence interval (CI) may be provided as the corresponding measure of dispersion. Likewise, when the appropriate (or desired) measure of centrality is the median, the corresponding dispersion measure to be provided may be the interquartile range or the combination of first and third quartiles, also referred to as 25th and 75th percentiles.

For the presentation of statistical results, standard approaches to determining significant digits will be used. Minimum and maximum values will be presented with the precision of the original values. Means, CIs, medians, interquartile ranges, and quartiles/percentiles will be rounded to 1 decimal place greater than (i.e., to the left of) the precision of the original value. Standard deviations will be rounded to 2 decimal places greater than the precision of the original value.

Percentages will be rounded to the nearest whole number, with values of “<1%” and “>99%” displayed for percentages approaching 0% and 100%, respectively. P-values will be presented with 3 decimal places of precision, and values less than 0.001 will be presented as “<0.001”.

## 7 SUMMARY OF THE STUDY POPULATION

All summaries of the study population, as presented in tables or figures, will display descriptive statistics derived for each patient cohort (dose level) and all patients combined (see **Appendix 2** for proposed data summaries). Moreover, for most patient characteristics/outcomes described below, patient-level data listings will be provided to disclose detailed information.

### 7.1 Patient Screening, Enrollment, and Disposition

For patients in the Screened and Safety Populations, several summaries will be generated. In a single table, an overview of screening, enrollment, and disposition outcomes will be provided, including:

- Total number of screened patients.
- Numbers and percentages of screened patients representing screening failures by primary reasons for failed study entry, which will include:
  - Determination of inclusion criteria not met.
  - Determination of exclusion criteria met.
  - Determination of inclusion criteria not met and exclusion criteria met.
  - Patient withdrawal of consent for participation.
  - Patient lost to follow-up.
  - Other (e.g., continued non-bleeding status or delayed infusion due to stopped or suspended study status).
- Number and percentage of screened patients who were enrolled in the study.
- Numbers and percentages of enrolled patients who were classified as:
  - Evaluable (by completing the Day-6 visit).
  - Completed the study (by completing the Day-30 visit).
  - Discontinued the study (by discontinuing participation prior to the Day-30 visit) by reasons for discontinuation, which will include:
    - Adverse event.
    - Death.
    - Lost to follow-up.
    - Non-compliance by patient.
    - Physician decision.
    - Pregnancy.
    - Protocol deviation.
    - Site terminated by sponsor.
    - Study terminated by sponsor.
    - Withdrawal by patient.
    - Other.

In a second table, the numbers and percentages of patients included in each analysis population (Screened, Safety, and Evaluable), as well as each subgroup within the Safety Population, will be

presented. A patient flow chart will also be constructed to display the total numbers of patients screened, excluded from the study (representing screening failures), enrolled in the study, deemed “evaluable”, and classified as either having completed or discontinued the study. Lastly, data describing enrollment and discontinuation statuses will be provided in separate patient-level data listings.

